#### **Inclusion criteria**

To participate in the interview aspect of this study, patients must meet the following criteria:

- Participant has a clinical diagnosis of **bilateral nasal polyps** as diagnosed by endoscopy or CT scan;
- Participant is aged 18 or over;
- Participant has severe nasal polyps symptoms defined as an patient-reported nasal obstruction VAS score of >5 (see Appendix 1);
- Participant has had at least **one previous surgery in the past ten years** for the **removal of nasal polyps**. Surgery in this case is defined as any procedure involving instruments with resulting incision and removal of polyp tissue from the nasal cavity (polypectomy);
- Participant is currently an eligible candidate for polypectomy defined by:  
An overall patient-reported VAS symptom score of >7.(**Appendix 2**), **AND**

An endoscopic bilateral nasal polyp score of at least 5 out of a maximum score of 8 (with a minimum score of 2 in each nasal cavity). (

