The patient experience of nasal polyps is typically assessed via clinical interview and review of clinical history and the use of existing patient-reported outcome instruments (PROs). PRO instruments used with patients with nasal polyps typically include single item visual analogue scales (VAS), whereby patients are asked to evaluate overall symptom severity, or the severity of individual symptoms of nasal polyps along a continuum, typically of 10cm or 100 mm whereby 0 represents 'no symptom' and '10 or 100 represents 'as bad as you can imagine', Scores of 0-3 (or 0-30) are defined as mild disease, >3-7 (or >30-70) as moderate disease and >7-10 (or >70-100) as severe disease. Historically, these items have not been developed based on patient characterization and therefore there is a need to understand the appropriateness of these measures for use within this population. The Sino-Nasal Outcomes Test (SNOT-22) is also used frequently within clinical research and as a clinical trial endpoint to measure health-related quality of life associated with rhinosinusitis with or without nasal polyps. The SNOT-22, a derivative of the SNOT-20, is a modification of the 31-Item Rhinosinusitis Outcome Measure (RSOM), containing 22 nose, sinus, and general health-related quality of life (HRQoL) items. Within the SNOT-22 patients are required to indicate the level of to which each listed nasal, sinus or HRQoL experience has been affected on a 6-point scale ranging from 0 (No problem) to 5 (Problem as bad as it can be) and also identify the five most important items affecting their health. Existing evidence supports the psychometric validity of the SNOT-22 among patients with rhinosinusitis; with evidence of high reliability and sensitivity to clinical change. Preliminary searches, however, suggest that evidence regarding the content validity of the SNOT-22 may be lacking.

GlaxoSmithKline (GSK) is embarking on a clinical program to assess treatment of severe, recurrent nasal polyps with an anti-interleukin-5 (anti-IL5) (mepolizumab). Patient symptomatic endpoints will form the basis for the assessment of treatment benefit of nasal polyp therapies. Currently, there is a lack of published qualitative data regarding nasal polyps to understand the symptoms (specific symptoms, duration,

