#### **3.2.1.1 Inclusion Criteria**

Participants will be required to meet the following inclusion criteria to be eligible for inclusion in the study.

1. Participant has a clinical diagnosis of **bilateral nasal polyps** as diagnosed by endoscopy or CT scan;
2. Participant is aged 18 or over;
3. Participant has severe nasal polyps symptoms defined as a patient-reported nasal obstruction VAS score of >5 (Appendix 1);
4. Participant has had at least **one previous surgery in the past ten years** for the **removal of nasal polyps**. Surgery in this case is defined as any procedure involving instruments with resulting incision and removal of polyp tissue from the nasal cavity (polypectomy);

5. Participant is currently an eligible candidate for polypectomy defined by:

a) An overall patient-reported VAS symptom score of  $>7$ . (**Appendix 2**), **AND**

An endoscopic bilateral nasal polyp score of at least 5 out of a maximum score of 8 (with a minimum score of 2 in each nasal cavity). (

- b) Appendix 3);
- 6. Participant has symptoms consistent with chronic rhinosinusitis;
- 7. Participant is currently received intranasal corticosteroids for the management of their nasal polyps;
- 8. Participant is willing to participate in the study and provide informed consent;
- 9. Participant is an English speaker and is able to read, write and fully understand the English language;
- 10. Participant is willing to and able to attend and participate in a 120-minute interview to discuss their experiences of nasal polyps and obtain their feedback on several symptom/impact questionnaires.

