## 9 APPENDICES

### Appendix 1: Patient-reported nasal obstruction VAS

The following question should be completed by the participant. Recruited participants are required to have an **overall symptom score of >50**.

[figure not shown]

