**Please rate your nasal obstruction at its worst over the previous 24 hours.**

## Appendix 2: Patient-reported overall symptom VAS

The following question should be completed by the participant. Recruited participants are required to have an **overall symptom score of >70**.

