**Please rate your nasal polyps symptoms at their worst over the previous 24 hours.**

[figure not shown]

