**Appendix 4: Case Report Form**

**PARTICIPANT CASE REPORT FORM (CRF)**

**TO BE COMPLETED BY THE RECRUITING PHYSICIAN**

**(Please complete a separate form for each patient recruited to the study)**

Physician Details	
Name (printed):	_____
Date of form completion:	
 
/___/___ Month
 
/___/___ Day
 
/___/___ Year
 

What is your job title/field of specialty?	
Please specify: _____	
Please sign here: _____	

INCLUSION CRITERIA		
	Yes	No
1. Participant has received oral or injectable systemic corticosteroids in the last 4 weeks (28 days) for the management of their nasal polyps	 1	 2
2. Participant has a clinical diagnosis of bilateral nasal polyps as diagnosed by endoscopy or CT scan.	 1	 2
3. Participant is aged 18 or over.	 1	 2
4. Participant has severe nasal polyp symptoms as defined as a patient-reported nasal obstruction Visual Analogue Score (VAS) of >5 (Please ask patient to complete Appendix 1 of this protocol).	 1	 2
5. Participant has had at least one previous surgery in the past ten years for the removal of nasal polyps . Surgery in this case is defined as any procedure involving instruments with resulting incision and removal of polyp tissue from the nasal cavity (polypectomy).	 1	 2
6. Participant is currently an eligible candidate for polypectomy defined by:		
c) An overall patient-reported VAS symptom score of >7 ( Appendix 2 of this protocol).	 1	 2
AND		
d) An endoscopic bilateral nasal polyp score of at least 5 out of a maximum score of 8 (with a minimum score of 2 in each nasal cavity) (	 1	 2

ADELPHI VALUES

INCLUSION CRITERIA		
	Yes	No
e) Appendix 3 of this protocol).		
7. Participant has symptoms consistent with chronic rhinosinusitis.	 1	 2

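### Do the VAS eligibility cut-offs of >5 and >7 in the criteria and CRF conflict with >50 and >70 on the VAS pages they cite?

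*Combined protocol and SAP*

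**What the plan says.** The two VAS eligibility cut-offs each appear in four places.

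- **Protocol synopsis, inclusion criteria:** nasal obstruction >5, citing Appendix 1, and "An overall patient-reported VAS symptom score of >7", citing Appendix 2. Neither has a scale.
- **Section 3.2.1.1, items 3 and 5a:** the same figures, again without a scale. Item 3 reads "patient-reported nasal obstruction VAS score of >5 (Appendix 1", and item 5a points to Appendix 2.
- **Appendix 4 (CRF), inclusion items 4 and 6c:** item 4 is "Participant has severe nasal polyp symptoms as defined as a patient-reported nasal obstruction Visual Analogue Score (VAS) of >5" and asks the physician to have the patient complete Appendix 1. Item 6c gives >7 and refers to Appendix 2.
- **Appendices 1 and 2, the VAS pages:** Appendix 1 requires an "overall symptom score of >50" and Appendix 2 an "overall symptom score of >70".

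Appendix 1 is titled as the nasal obstruction VAS, and its item is "Please rate your nasal obstruction at its worst over the previous 24 hours". The overall item, "Please rate your nasal polyps symptoms at their worst over the previous 24 hours", belongs to Appendix 2.

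Section 1 describes these instruments as usually 10 cm or 100 mm long and gives the severity bands in both notations: "Scores of 0-3 (or 0-30) are defined as mild disease, >3-7 (or >30-70) as moderate disease and >7-10 (or >70-100) as severe disease". The interview versions of the two items in Appendices 7 and 8 run from 0 to 100.

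**The concern.** The CRF is a working form. A physician ticks Yes or No against each criterion, and all-Yes inclusion answers with all-No exclusion answers bring the patient in. If the form states >5 and the patient marks a line running from 0 to 100, the form read literally sets a threshold one tenth of the one on the VAS page. The same holds for >7 against >70. The study is meant to describe patients with severe, recurrent disease who resemble the sponsor's trial population, so a loosened screen would weaken that claim. The CRF shown has no field for the score itself, so a misreading could not be traced from that form.

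The label in Appendix 1 is a second matter, which conversion does not resolve. Taken word for word, the two VAS pages give two thresholds for an overall symptom score and none for nasal obstruction.

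**Working it through.** No sample size, power or error rate depends on this point, so the check is whether the statements give one rule or two.

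**Step 1: count the statements.** Without a scale: 2 cut-offs × 3 places (synopsis, Section 3.2.1.1, CRF) = 6. In 0-100 figures: 2 (Appendices 1 and 2). Total 6 + 2 = 8.

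**Step 2: conversion factor.** From the paired bands in Section 1: 30/3 = 10, 70/7 = 10, 100/10 = 10.

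**Step 3: convert the cut-offs.**

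- Obstruction: 5 × 10 = 50. Appendix 1 prints 50. Difference 50 − 50 = 0.
- Overall symptoms: 7 × 10 = 70. Appendix 2 prints 70. Difference 70 − 70 = 0.

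**Step 4: apply the statements together on a 0-100 line.** For a score x, requiring both x > 5 and x > 50 is the same as requiring x > 50. Requiring both x > 7 and x > 70 is the same as requiring x > 70. A physician who follows the form to the page it cites therefore arrives at the larger figure, with or without converting.

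**Step 5: size of the one possible error.** It needs someone to use the CRF figure on a 0-100 line and disregard the threshold printed on the VAS page.

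- Obstruction: 100 − 5 = 95% of the line would pass, against 100 − 50 = 50%.
- Overall symptoms: 100 − 7 = 93%, against 100 − 70 = 30%.

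These are lengths of scale under a misreading, not shares of patients. Each also treats one criterion alone, whereas both VAS cut-offs and the endoscopic score must be met.

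**Step 6: the Appendix 1 label.** The page's title and only question concern nasal obstruction, so the patient's mark on it is an obstruction score. If >50 were really meant for the overall score, it would be redundant, because Appendix 2 already requires that score to exceed 70. Both facts point to a wrong word and not to a different rule.

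**Step 7: what depends on it.** Sections 3.3.1 and 3.5 state that there are no formal endpoints or hypotheses. Section 3.4 bases the sample of 30 on conceptual saturation. The VAS scores summarised under Section 4 are those completed in the interview, not the screening scores.

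One argument should not be used. It is tempting to say that the severity bands rule out the literal reading because it would admit mild or moderate scores. For obstruction this fails, since a cut-off of 50 already admits scores of 51 to 70, which Section 1 places in the moderate band. The argument works only for the overall score.

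**The case for a change.** The strongest case for acting is that the conversion has to be inferred. The pairing of scales sits in a background section that describes typical instruments and is not part of the form. Recruiting physicians include primary care doctors as well as ENT specialists. The CRF records only Yes or No. The scale figures in Appendices 1 and 2 are not visible in the text available, so whether they print end-points cannot be confirmed; the 0-100 range is inferred from the printed thresholds and the interview versions of the items. The edits would be cheap.

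Part of this stands. The notation is inconsistent and the Appendix 1 label is wrong. A sponsor reissuing these forms for another reason could tidy both, moving neither cut-off.

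It does not show that anyone would be screened differently. The physician need not consult the background section, because the page used to obtain the score carries its own threshold. The physician's tick is also not the last step: the recruitment agency screens the participant, and the interviewer is told to check the CRF, the screener and eligibility beforehand. The documents do not show whether those checks would catch a VAS misreading, so they offer only modest reassurance. Adding numeric score fields to the CRF would be a preference; no planned analysis needs them.

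**Conclusion.** The inconsistency is real but clerical, and no change to the plan is called for. Eight statements express two cut-offs in two notations, with a gap of zero under the plan's own factor of ten, and one of the two VAS pages carries a wrong label. Followed as written, the forms lead to the thresholds printed on the VAS pages. No effect on enrolment is shown, and the sample size, the analysis and the study's conclusions do not depend on the notation.

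This rests on two assumptions: that the screening VAS runs from 0 to 100, as the printed thresholds and the interview versions imply, and that physicians use the cited pages to obtain the scores, as the CRF directs for item 4 and indicates by reference for item 6c. The share of patients affected if either failed cannot be computed from the documents.

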**INFORMATION ABOUT THE PARTICIPANT'S NASAL POLYPS**

1. When was the participant first diagnosed with bilateral nasal polyps?

\_\_\_\_\_/\_\_\_\_ (month, year)

2. Please specify which methods were used to support the participant's diagnosis with nasal polyps:

Endoscopy 1

CT scan 2

Nasoscope investigation 3

MRI scan 4

Other diagnosis tool (please state) 5

---

3. Please indicate which of the following symptoms the participant experienced with their nasal polyps (tick as many as apply):

Nasal blockage/obstruction/congestion 1

Nasal discharge (anterior) 2

Post nasal drip (anterior discharge) 3

Facial pain 4

Facial pressure 5

Reduction or loss of smell 6

Reduction or loss of taste 7

Sleep apnea 8

Snoring 9

Other symptom type (please state) 10

---

4. Please indicate the number of surgeries the patient has received to **remove** their nasal (polypectomy), the date of surgery and the extent of the surgery received.

ADELPHI VALUES

Surgery Number	Date of surgery (MM/DD/YYYY)	Type of nasal polyp surgery (e.g. polypectomy, functional endoscopic sinus surgery with polypectomy or balloon sinuplasty with polypectomy etc.)

5. Please indicate what treatments (drug and non-drug treatments) the participant is currently receiving (or has previously received) for their nasal polyps.

	Current medications		Past medications		
Treatments (for medications, generic or trade name is acceptable)  Please specify type and dose	Medication in current use? (✓)	Medication start date (MM/DD/YYYY)	Medication NOT in current use, BUT used in the past? (✓)	Medication start date (MM/DD/YYYY)	Medication end date (MM/DD/YYYY)
Nasal corticosteroids  (e.g., Flutisone, Budesonide, Flunisolide, Mometasone etc.)					

ADELPHI VALUES

Treatments (for medications, generic or trade name is acceptable)  Please specify type and dose	Current medications		Past medications		
	Medication in current use? (✓)	Medication start date (MM/DD/YYYY)	Medication NOT in current use, BUT used in the past? (✓)	Medication start date (MM/DD/YYYY)	Medication end date (MM/DD/YYYY)
Oral corticosteroids (e.g., Prednisone)					
Injectable corticosteroids (e.g., Prednisone)					

ADELPHI VALUES

Treatments (for medications, generic or trade name is acceptable)  Please specify type and dose	Current medications		Past medications		
	Medication in current use? (✓)	Medication start date (MM/DD/YYYY)	Medication NOT in current use, BUT used in the past? (✓)	Medication start date (MM/DD/YYYY)	Medication end date (MM/DD/YYYY)
Other treatment type (please specify)					

6. Please indicate which surgical **nasal** treatments (**which did not include the removal of polyps**) that the patient has previously received.

Other nasal and/or sinus surgery ( Non-polyp removal surgeries )	Dates of previous surgeries (please list all dates if the surgery has been performed more than once)
(e.g., balloon sinuplasty without polypectomy, nasal stent insertion)	

**GENERAL HEALTH STATUS INFORMATION**

7. Does the participant currently have any chronic diseases or conditions in addition to bilateral nasal polyps?

1 Yes                      0 No

If **YES**, please indicate the disease(s) or condition(s) below. For each comorbidity, please indicate the category of the chronic disease or condition the participant has and the specific diagnosis.

Chronic Disease/Condition	Please specify diagnosis
 1 Cardiovascular	
 2 Urological/Nephrological	
 3 Dermatological	
 4 Endocrinological/Nutritional	
 5 Gastroenterological	
 6 Gynecological	
 7 Psychiatric	
 8 Stomatological (diseases of the mouth)	
 9 Ophthalmological	
 10 Hematological	
 11 Pneumological/Pulmonary	
 12 Rheumatological	
 13 Neurological	
 14 Allergy	
 15 Otorhinolaryngological (ear, nose, throat)	
 16 Other (e.g. obesity)	

8. Is the participant currently taking treatment(s) for any other disease or condition?

1 Yes

0 No

9. If yes, please give the name of the condition and the treatment received.

Disease or Condition	Treatment
 1	
 2	
 3	
 4	
 5	
 6	

10. How would you rate the participant's general health?

Excellent 1

Very Good 2

Good 3

Fair 4

Poor 5

Once you have a participant who has agreed to participate in the study and who meets the selection criteria, please send a signed copy of this form

to **MedQuest** by fax  PPD for the attention of:  PPD

Should you have any questions, please contact  PPD on  PPD

**THANK YOU FOR COMPLETING THIS FORM**

Approved:

**Appendix 6: Patient Demographic Form**

ADELPHI VALUES

**DEMOGRAPHICS FORM**

This form is to be completed by the recruitment agency  
(Please complete a separate form for each participant recruited)

**ACTIVITIES**

Please ask the participant which activities they would like to take part in:

- 60-minute interview ONLY 1
- 60-minute interview AND 10-day app activity and follow-up call to provide feedback \* 2

If the participant does not want to participate in the app task, please skip straight to the demographic questions section below.

\*If the participant **DOES** want to take part in the app task, please ensure that they meet the following inclusion criteria

INCLUSION CRITERIA FOR APP TASK	YES	NO
4. Participant owns/or has access to either a smartphone (iOS or android) or tablet which has video, audio/microphone and photographic capabilities and access to either the Apple app store or google play store to download the app;	 1	 1
5. Participant is willing and able to take part in the real-time data application task and respond to a series of questions/tasks fielded to them via the application over the course of 10 days.  AND  Is willing to respond to some brief questions following the real-time data capture task about their experience of using the app and completing the tasks, either during their interview or in a 5-10 minute telephone call following completion of the task	 1	 2
6. Participant has stated that they would feel comfortable recording short videos of themselves and providing audio commentary in response to questions/tasks.	 1	 2

Date:   /   / 2017  
MM DD

Center Number: /\_\_\_/\_\_\_/

Participant N°: /\_\_\_/\_\_\_/

ADELPHI VALUES

👉 If **ONE** of the above answers is **NO**, the patient **CANNOT** be included in the app task aspect of the study.

**DEMOGRAPHICS QUESTIONS**

Please complete the following questions for all participant irrespective of which research activities they would like to take part in.

1. How old are you? |\_\_|\_\_| years

2. What is your gender?

Male 1

Female 2

3. How long have you have you been experiencing symptoms of nasal polyps?

\_\_\_\_\_years\_\_\_\_\_ months

4. At what age were you first diagnosed with nasal polyps by a physician?

\_\_\_\_\_ years\_\_\_\_\_ months

5. Who diagnosed your nasal polyps?

Ear, nose and throat (ENT) specialist 1

GP/Family doctor 2

Other (please specify)\_\_\_\_\_ 3

6. What is your ethnicity? (please check which applies)

Hispanic or Latino (of any race) 1

Non-Hispanic or Latino 2

7. What is your race? (please check one box only)

White 1

Black/African American 2

Date:  /  / 2017  
MM DD

Center Number: /\_\_\_/\_\_\_/

Participant N°: /\_\_\_/\_\_\_/

ADELPHI VALUES

- Asian or Pacific Islander  3
- Native American or Alaska native  4
- North African or Middle Eastern  5
- Multi-racial  6
- (Please specify) \_\_\_\_\_
- Other  7
- (Please specify) \_\_\_\_\_

**8. What is your highest level of education?**

- Grade school  1
- Some high school  2
- High school diploma or GED  3
- Some years of college  4
- Certificate program  5
- College or university degree (2 or 4 year)  6
- Graduate or professional degree  7
- Other (please specify) \_\_\_\_\_  8

**9. What is your current living status? (please check all that apply)**

- Living alone  1
- Living with husband/wife/partner  2
- Living with parents  3
- Living with your children  4
- Living with other family members  5
- Living with your friends  6
- Other (please specify) \_\_\_\_\_  7

**10. How would you describe your work status (Please check all that apply)**

- Working full-time  1

Date:  /  / 2017  
MM DD

Center Number: /\_\_\_/\_\_\_/

Participant N°: /\_\_\_/\_\_\_/

Working part-time

\_2

Retired

\_3

Unemployed

\_4

Student

\_5

Other (please specify) \_\_\_\_\_

\_6

ADELPHI VALUES

**11. What is your approximate annual income?**

Under \$25,000 \_1

\$25,000 to \$50,000 \_2

\$50,000 to \$75,000 \_3

\$75,000 to \$100,000 \_4

More than \$100,000 \_5

Prefer not to answer \_6

**12. How would you rate your health in general?**

Excellent \_1

Very Good \_2

Good \_3

Fair \_4

Poor \_5

**Recruitment Quotas**

In addition to meeting the inclusion/exclusion criteria please ensure the following quotas are met by the sample:

Participant characteristics		Adults		Total
		18-45	46+	
Age		≥6	≥6	≥12
Gender	Male	≥2	≥2	≥6
	Female	≥2	≥2	≥6
Ethnicity	Hispanic or Latino (of any race)			≥6
	Non-Hispanic or Latino			≥6
Race	White			≥4
	Black/African American			≥4
	Multi-racial			≥2
	Other race/ethnicities 
 
• Asian or Pacific Islander
 
• Native American or Alaska native
 
• North African or Middle Eastern
 
• Other (specified by participant)
 
			≥2
Education	Some high school			≥3
	College or higher			≥3
Polypectomy surgery	In past 2 years			≥6
	In past 3-10			≥6

**Recruiter:** If the participant meets the inclusion criteria for the study and is appropriate based on the sample quotas above please schedule the participant for an interview.

